7.5. Electrocardiogram Results

A listing of safety ECG results will be provided including treatment, assessment date and time, and ECG results.

7.6. Other Safety Measures

A data listing will be provided for subjects experiencing pregnancy during the study.

7.7. Changes From Protocol-Specified Safety Analyses

No change from the protocol-specified safety analysis is planned.

8. PHARMACOKINETIC ANALYSES

The following listings will be provided for predose and postdose PK analysis for subjects in the PK analysis set:

- Listing of PK sampling details
- Listing of study drug administration record for PK dosing.

9. PATIENT REPORTED OUTCOMES

The patient reported outcome (PRO) questionnaires include:

- Visual Analog Scale (VAS) adherence questionnaire for HIV study treatment;
- HIV Treatment Satisfaction Questionnaire (HIV-TSQ) (status form assessed at Study Day 1, and change form at other visits)
- Short Form-36 (SF-36) Version 2 Health Survey.
- FACIT-F
- CLDQ-HCV
- WPAI: Hepatitis C

PRO data will be summarized for the subjects in the safety analysis set. All PRO data collected up to 30 days after subjects who permanently discontinued all study drug will be summarized by treatment group.

Unless otherwise stated, multiple responses and out of range responses will be set to missing and missing responses will not be imputed. The PRO data will be listed.

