3.4. Duration of Treatment

The HIV treatment duration is from the Day 1 visit until the last study visit at the Post-HCV Treatment Week 12. The HCV treatment duration is 12 weeks. Screening assessments will be completed within 42 days of the Day 1 visit.

All subjects will complete the following study visits: Screening, Day 1, Weeks 4, 6 (laboratory visit only), 8 (start of HCV treatment), 12, 16, and 20 (end of HCV treatment), and post-HCV treatment visits 4 and 12 weeks after the last LDV/SOF dose.

Subjects who complete the study through the last study visit at the Post-HCV Treatment Week 12 visit will be required to return to the clinic 30 days after the completion of the study treatment for a 30-Day Follow-Up visit.

- a Following the Day 1 visit, subjects will return for study visits at Weeks 4, 6 (laboratory visit only), 8, 12, 16, 20, and Post-HCV Treatment 4 and 12 weeks after the last LDV/SOF dose.
- b Part 1: subjects are randomized to either E/C/F/TAF FDC or F/R/TAF FDC on Day 1 and maintain HIV treatment to the Week 8 visit.
- c Part 2: At Week 8, once HIV-1 RNA suppression (< 50 copies/mL) is confirmed (based on the Week 6 HIV-1 RNA value), subjects will start on LDV/SOF FDC for 12 weeks (until Week 20) while maintaining their HIV treatment. At Week 20, LDV/SOF FDC will be discontinued while continuing HIV treatment. Subjects will continue in the study for another 12 weeks to determine SVR4 (4 weeks post-HCV treatment) and SVR12 (12 weeks post-HCV treatment).

- d Subjects who complete the study through the Post-HCV Treatment Week 12 visit will be required to return to the clinic 30 days after the completion of the study treatment for a 30-Day Follow-Up Visit.
- e At the Day 1 visit, subjects will switch to either E/C/F/TAF FDC or F/R/TAF FDC and continue on HIV treatment until the last study visit at the Post-HCV Treatment Week 12 visit.

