6.4.2. HIV Treatment and Post-HCV Treatment Assessments (Post-HCV Treatment Weeks 4 and 12)

The following evaluations are to be completed at the end of 4 and 12 weeks after completion of HCV treatment (Post-HCV Treatment Weeks 4 and 12 visits, respectively) and should be timed from the date of last administration of the HCV treatment. The Post-HCV Treatment Week 4 visit is to be completed \pm 2 days, and the Post-HCV Treatment Week 12 visit is to be completed within \pm 4 days; however, unless notified by Gilead Sciences, the Post-HCV Treatment Week 4 and 12 should be completed within 2 and 4 days of the protocol-specified visit date, respectively.

All subjects must complete the Post-HCV Treatment Weeks 4 and 12 visits. The end of study will occur at the Post-HCV Treatment Week 12 visit.

The following assessments are to be completed:

- Review AEs and changes in concomitant medications
- Complete physical examination (**Post-HCV Treatment Week 12 only**) (urogenital/anorectal exams will be performed at the discretion of the Investigator)
- Perform symptom-directed physical examination as needed
- Obtain vital signs, including weight
- Obtain urine samples for the following laboratory analyses:
 - Urinalysis and urine chemistry
 - Urine pregnancy test (females of childbearing potential only); positive urine pregnancy tests will be confirmed with a serum test. If the serum test is positive, the subject will be discontinued.
 - Renal tubular function assessments (Post-HCV Treatment Week 12 only)
 - Urine sample storage for possible additional clinical testing
- Obtain blood samples for the following laboratory analyses:
 - Chemistry profile
 - Hematology profile
 - Coagulation assessments
 - Metabolic assessments (Post-HCV Treatment Week 12 only)

- CD4+ cell count
- Plasma HIV-1 RNA
- Plasma HCV RNA
- Serum bone safety assessments (Post-HCV Treatment Week 12 only)
- Platelet and coagulation function assessments (Post-HCV Treatment Week 12 only)
- Inflammation assessments (Post-HCV Treatment Week 12 only)
- Plasma storage samples for virology, safety, and/or PK testing
- Serum storage sample for possible additional clinical testing

- PPD

- Obtain estimated glomerular filtration rate according to the Cockcroft-Gault formula (see Section 4.2 for details)
- Complete questionnaires (Post-HCV Treatment Week 12 only): subject is to read questionnaire by her/himself and write/mark answers directly onto the questionnaires.
 - VAS for HIV adherence

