6.5. Post-treatment Assessments

6.5.1. Early Study Drug Discontinuation (ESDD) Visit

Early study drug discontinuation during Part 1 (Day 1 through Week 8):

If the subject discontinues HIV study drug dosing in Part 1, the subject will be discontinued from the study and will not continue to Part 2 of the study. The subject will be asked to return to the clinic within 72 hours of stopping HIV study drugs for the ESDD visit, followed by the 30-Day Follow-Up visit.

Early study drug discontinuation during Part 2 (after initiation of HCV treatment):

If the subject discontinues HCV study drug dosing only prior to completing the 12-week HCV treatment, the following will occur:

- Be asked to return to the clinic within 72 hours of stopping HCV study drug for the ESDD visit.
- Remain in the study to return for follow-up visits 4 and 12 weeks after the last dose of LDV/SOF, as described in Section 6.4.2.
- Continue to receive HIV study drugs (see ESDD procedures below).

If the subject discontinues HIV study drug dosing only, the following will occur:

- Be asked to return to the clinic within 72 hours of stopping HIV study drugs for the ESDD visit.
- HIV regimen may be changed, after discussion with the Medical Monitor. The new HIV regimen should be designed to allow continued dosing of LDV/SOF. LDV/SOF should be continued unless an HIV regimen cannot be constructed that would allow coadministration with the new HIV regimen.
- Remain in the study to complete the 12-week HCV treatment (see Section 6.4.1) and follow-up visits 4 and 12 weeks after the last dose of LDV/SOF, as described in Section 6.4.2.

If the subject discontinues both HIV and HCV study drug dosing, the following will occur:

- Be asked to return to the clinic within 72 hours of stopping study drugs for the ESDD visit.
- Remain in the study to return for follow-up visits 4 and 12 weeks after the last dose of LDV/SOF, as described in Section 6.4.2.

At the ESDD Visit, any evaluations showing abnormal results indicating that there is a possible or probable causal relationship with the study drugs, should be repeated weekly (or as often as deemed prudent by the Investigator) until the abnormality is resolved, returns to baseline, or is otherwise explained.

The following evaluations are to be completed at the ESDD Visit:

- Review of AEs and changes in concomitant medications

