Appendix 2.Study Procedures Table

			End of Week ^c		End of Week ^c – Part 2							
			Pa On Tro	rt 1 eatment	C	n Tre	eatme	nt	Post-HCV	Treatment	30-Dav	
	Screening ^a	Day 1 ^b	4	6	8	12	16	20	4	12	Follow-Up ^d	ESDD ^e
Written Informed Consent	Х											
Medical History	Х											
Liver Cirrhosis Determination	Х											
Concomitant Medications	Х	Х	Х		Х	Х	Х	Х	Х	Х	Х	Х
Adverse Events	Х	Х	Х		Х	Х	Х	Х	Х	Х	Х	Х
Complete Physical Examination	Х	Х								Х		Х
Symptom-Directed Physical Examination ^f			Х		Х	Х	Х	Х	Х		Х	
Vital Signs & Weight	Х	Х	Х		Х	Х	Х	Х	Х	Х	Х	Х
Height	Х											
12-Lead ECG (performed supine)	Х											Х
Urinalysis & Urine Chemistry	Х	Х	Х		Х	Х	Х	Х	Х	Х	Х	Х
Urine Storage Sample		Х	Х		Х	Х	Х	Х	Х	Х		Х
Urine Pregnancy Test ^g		Х	Х		Х	Х	Х	Х	Х	Х	Х	Х
Serum Pregnancy Test ^g	Х											
Chemistry Profile ^h	Х	Х	Х		Х	Х	Х	Х	Х	Х	Х	Х
Hematology Profile ⁱ	Х	Х	Х		Х	Х	Х	Х	Х	Х	Х	Х
Coagulation Assessments ^j	Х	Х	Х		Х	Х	Х	Х	Х	Х		
Metabolic Assessments ^k		Х			Х			Х		Х		
CD4+ Cell Count	Х	Х	Х		Х	Х	Х	Х	Х	Х	Х	Х
Plasma HIV-1 RNA	Х	Х	Х	X	Х	Х	Х	Х	Х	Х	Х	Х
HIV-1 Proviral Genotype ¹	X											
HIV-1 Genotype/Phenotype ^m												Х

			End of	f Week ^e			End	of W	eek ^e – Part 2	2		
			Pa On Tr	rt 1 eatment	C	n Tro	eatme	nt	Post-HCV	Treatment	30-Dav	
	Screening ^a	Day 1 ^b	4	6	8	12	16	20	4	12	Follow-Up ^d	ESDD ^e
Plasma HCV RNA	X	X			Х	Χ	Х	X	Х	Х	Х	X
HCV Genotype & Subtype	Х											
HCV IL28B Genotype	Х											
HIV, HBV & HCV Serologies ⁿ	X											
Evaluations of Bone & Renal Safety, Inflammation and Platelet and Coagulation Function [°]		x	X		x	х		x		X		Х
Plasma Storage Sample ^p		X	Х	X	Х	Х	Х	Х	Х	Х		Х
Serum Storage Sample ^p	÷ .	X	Х		Х	Х	Х	Х	X	X		Х
PPD		X	Х		Х			Х		Х		Х
Estimated GFR _{CG} ^r	X	X	Х		Х	Х	Х	Х	Х	Х		Х
Population PK ^s			Х		Х	Х	Х	Х				
Health Related Questionnaires ^t		X			Х			Х		Х		Х
Randomization		X					2.					
Study Drug Dispensation and Accountability ^u	· · · · · · · · · · · · · · · · · · ·	x	X		Х	X	Х	X	X	X		X ^v

a Evaluations to be completed within 42 days prior to the Day 1 visit

b Subjects will be dispensed HIV study drugs only at the Day 1 visit; initiation of HIV treatment with the study drugs must take place within 24 hours after the Day 1 visit.

c All study visits are to be scheduled relative to the Day 1 visit date. Visit windows are ± 2 days of the protocol specified date through Post-HCV Treatment Week 4 visit, and ± 4 days of the protocol specified date at Post-HCV Treatment Week 12.

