7.1.1. Administration Periods for Safety Analysis

In the 2-part coinfection study, subjects receive different treatments at different periods of the study (Figure 7-1). Four administration periods, Part 1, Part 2, Co-administration, and Whole Study, are defined accordingly in Table 7-1 with start, end, and safety cutoff dates provided.

Figure 7-1. Study Treatments Received in Different Periods of Study

- a In Part 1 of the study, subject receive HIV study drug only.
- b Part 2 is applicable only if subjects took at least one dose of LDV/SOF.
- c Subjects who entered Part 2 receive both LDV/SOF and HIV study drug for at most 12 weeks and this is defined as the co-administration period. The co-administration period is terminated by permanent discontinuation of LDV/SOF or HIV study drug, which ever happens earlier;
- d By the end of co-administration period, if subject permanently discontinued LDV/SOF while still receiving HIV drug, HIV study drug will continue to be administered until the end of Part 2 as planned in protocol. If subject prematurely discontinued HIV study drug while still receiving LDV/SOF, LDV/SOF will continue to be administered until 12 weeks of HCV treatment is completed. If subject permanently discontinued both LDV/SOF and HIV study drug at the same date, no study drug will be administered after the co-administration period until the end of Part 2.

	, ,	•				
Administration Period	Start Date	End Date	Safety Cutoff Date			
Part 1	HIV study drug first dose date	Minimum of HIV study drug last dose date and Part 2 Day 1	End date if subject is ever dosed with LDV/SOF; or end date + 30 days if subject is never dosed with LDV/SOF			
Part 2	HCV study drug first dose date if applicable	Maximum of HIV and HCV study drug last dose dates if applicable	30 days after Part 2 period end date			
Co-administration	HCV study drug first dose date if applicable	Minimum of HIV and HCV study drug last dose dates if applicable	30 days after Co-administration period end date			
Whole Study	HIV study drug first dose date	Maximum of HIV and HCV study drug last dose dates	30 days after Whole Study period end date			

Table 7-1. Start, End, and Safety Cutoff Dates of All Administration Periods

Summary of safety data is planned by administration periods as below:

- Adverse events and laboratory abnormalities will be summarized for Part 1, Co-administration, and Whole Study periods respectively.

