9.3. Analysis of SF-36, FACIT-F, CLDQ-HCV, and WPAI: Hepatitis C

The transformed scale scores (0 to 100 scale) at Study Baseline, Part 2 Baseline (Week 8), Week 20, End of HCV Treatment (EOT-HCV), FU-12, and EOT-HIV will be presented for each of the 8 domains of the SF-36 (physical functioning, role-physical, bodily pain, general health, vitality, social functioning, role-emotional, and mental health), and for the physical component summary and mental component summary. Following changes will also be presented in similar manner:

- Change from Study Baseline at each visit (if applicable),
- change from Part 2 Baseline at Week 20, EOT-HCV, and FU-12,
- change from EOT-HCV at FU-12.

Scoring of the SF-36 scales will be performed as described in Chapter 6 of the SF-36 Health Survey: Manual and Interpretation Guide, Version 2. A Wilcoxon signed rank test will be used to explore within treatment group changes described above.

The same analyses will be carried out for CLDQ-HCV (overall score), FACIT-F (trial outcome index and total score), and WPAI: Hep C (% overall work impairment due to HCV for subjects who worked in the past week and % activity impairment due to hepatitis C for all subjects), except that, EOT-HIV and change from Study Baseline as EOT-HIV will not be presented.

The calculation algorithms for CLDQ-HCV, FACIT-F, and WPAI:Hep C are described in Appendix 3.

For imputation of missing data in the QOL data, please refer to Section 3.6.1.5.

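### The 30-day PRO cut-off in SAP 9 leaves scheduled FU-12 questionnaires out of the summaries for Part 2 subjects whose last study-drug dose was more than 30 days before that visit

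*SAP*

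**What the plan says.** SAP 9 places the questionnaires in the safety analysis set and limits what is summarised: "All PRO data collected up to 30 days after subjects who permanently discontinued all study drug will be summarized by treatment group". The sentence is garbled. The natural reading is a limit of 30 days after permanent discontinuation of all study drug, which matches the safety rules in SAP 3.1.3.1 and 7.1. SAP Table 7-1 ends the whole-study period at the "Maximum of HIV and HCV study drug last dose dates" and sets the safety cut-off 30 days later. SAP 3 defines permanent discontinuation to include planned completion as well as early stopping.

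SAP 9.3 analyses SF-36 at FU-12 and applies the same analyses to FACIT-F, CLDQ-HCV and WPAI. The planned contrasts include "change from Part 2 Baseline at Week 20, EOT-HCV, and FU-12" and the change from end of HCV treatment to FU-12, explored with Wilcoxon signed-rank tests within treatment group. No exception to the cut-off is stated. SAP 3.6.1.5 does not impute missing FU-12 questionnaires, and SAP 3.8.3 assigns questionnaires to nominal visits with no analysis window.

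In the protocol, section 6.4.2 schedules the forms ("Complete questionnaires (Post-HCV Treatment Week 12 only") and says that the post-HCV visits "should be timed from the date of last administration of the HCV treatment". Appendix 2 gives a window of plus or minus "4 days of the protocol specified date at Post-HCV Treatment Week 12". For Part 2 subjects who stop both drugs, section 6.5.1 says: "Remain in the study to return for follow-up visits 4 and 12 weeks after the last dose of LDV/SOF, as described in Section 6.4.2". A subject who stops only HIV drug in Part 2 likewise stays to finish LDV/SOF and attend both follow-up visits.

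**The concern.** Two clocks are in use. FU-12 runs from the last LDV/SOF dose, and the cut-off runs from the later of the two last doses. FU-12 is always off LDV/SOF, so whether its form is summarised depends on how long HIV study drug was taken. That has no bearing on the change after HCV treatment that SAP 9.3 sets out to measure.

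The results are uneven. A subject who completes all 12 weeks of LDV/SOF on a replacement antiretroviral can lose the FU-12 form from the summary, while a subject who stops LDV/SOF early but stays on HIV study drug keeps it. SAP 3.1.2.2 retains HCV RNA collected after the last dose, so SVR12 and FU-12 quality of life would describe slightly different groups of treated subjects. The exclusion depends on treatment status, and no imputation or sensitivity analysis covers it.

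**Working it through.** The plan states no figure for this point, so the check is date arithmetic.

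**Inputs**
- FU-12: 12 weeks = 84 days after the last LDV/SOF dose, ±4 days, so FU Day 80 to 88 (Protocol 6.4.2 and Appendix 2). FU Day is counted from the last LDV/SOF dose (SAP 3.8.2.1).
- Cut-off: max(last HIV dose, last LDV/SOF dose) + 30 days (SAP 9, read with Table 7-1).
- Planned HIV dosing: "The HIV treatment duration is from the Day 1 visit until the last study visit at the Post-HCV Treatment Week 12" (Protocol 3.4).
- Nominal timeline, assumed: LDV/SOF from Study Day 57 to 57 + 84 − 1 = 140; FU-12 on 140 + 84 = 224.

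**Rule.** The form is summarised if the FU-12 date is no later than the cut-off. When HIV drug is the last drug taken, this requires a last HIV dose on or after FU Day 84 − 30 = 54. Over the visit window the threshold is 80 − 30 = 50 to 88 − 30 = 58.

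**Cases**

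| Pattern in Part 2 | Cut-off (Study Day) | FU-12 (Study Day) | FU-12 form summarised? |
|---|---|---|---|
| Completer, HIV drug to Day 224 | 224 + 30 = 254 | 224 | Yes |
| HIV drug stopped Day 100, LDV/SOF completed Day 140 | 140 + 30 = 170 | 224 | No |
| Both stopped Day 100 | 100 + 30 = 130 | 100 + 84 = 184 | No |
| HIV drug stopped FU Day 28 (Day 168) | 198 | 224 | No |
| HIV drug stopped FU Day 53 (Day 193) | 223 | 224 | No |
| HIV drug stopped FU Day 54 (Day 194) | 224 | 224 | Yes |
| HIV drug stopped FU Day 70 (Day 210) | 240 | 224 | Yes |
| LDV/SOF stopped Day 100, HIV drug to FU-12 (Day 184) | 184 + 30 = 214 | 184 | Yes |

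Subjects who stop HIV drug in Part 1 leave the study (Protocol 6.5.1) and have no FU-12 form.

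**How much of Part 2 is exposed.** With LDV/SOF completed on schedule, HIV drug could stop early on any of Study Days 57 to 223, which is 167 days. Stops on Days 194 to 223 (30 days) keep the form; the other 137 lose it, 137/167 = 82% (81.6% to 82.5% over the visit window). This is a share of calendar days, not of subjects.

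**Size of any bias.** If a share *f* of an arm's FU-12 forms is omitted and their mean change differs by *d* from the rest, the arm mean shifts by *f* × *d*. The documents give neither quantity. For scale only, one form is 1/60 = 1.7% of a planned arm of 60.

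**The case against.** The strongest case for leaving the rule alone has four parts.

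- **Consistency.** Questionnaires sit in the safety set and take that set's usual 30-day limit. HIV efficacy data are cut even closer, at last dose plus 1 day (SAP 6). A form completed on a replacement antiretroviral also reflects a non-study regimen, although the summaries are by HIV treatment group. This is a fair description of an on-treatment convention, but it fits FU-12 poorly: that visit is off LDV/SOF by design, and SAP 9.3 uses it to measure change after HCV treatment.
- **Importance.** Questionnaires are not among the primary or secondary endpoints (Protocol 3.1). They appear as an additional item in the synopsis, and the signed-rank tests are exploratory. This stands and limits the weight of the point.
- **Numbers.** Part 2 entrants have already passed 8 weeks of tolerability and HIV suppression. Protocol 1.3.2 reports no treatment stops for adverse events and no confirmed HIV rebound in the earlier coinfection study (ION-4). Protocol 1.2.2 reports virologic failure in 10 of 959 subjects switched to E/C/F/TAF. This also stands: few forms may be lost.
- **Other data.** Early-discontinuation questionnaires are due within 72 hours of stopping, and the forms are listed in any case. The former describe the moment of stopping, so they do not replace FU-12.

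A reader might infer more than the documents support. Not every early HIV-drug stopper is excluded: stops within 30 days before FU-12 are kept, and Part 1 stoppers have no form to lose. Nor do the summaries keep only subjects still on drug, since those late stoppers and subjects who stopped LDV/SOF alone remain. It is also tempting to say that the excluded subjects stopped for toxicity, failure or non-compliance and that the results will therefore flatter treatment. Protocol 6.7 also allows intercurrent illness and subject request, and Protocol 6.9.1 lets a subject with virologic failure but no detected resistance stay on HIV drug. A subject who changed regimen may have recovered by FU-12. No single point difference fits four differently scaled instruments, and a higher WPAI score is worse.

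**Conclusion.** The point holds in a limited form. Read as a limit of 30 days after all study drug stops, SAP 9 omits from the FU-12 summaries and signed-rank tests the SF-36, FACIT-F, CLDQ-HCV and WPAI forms of Part 2 subjects whose last dose of either study drug came before about FU Day 54 (50 to 58 over the visit window). The protocol requires those visits and collects those forms, and the same subjects' SVR12 data are retained. The conclusion rests on that reading of a garbled sentence, which the parallel safety rules support, and on the absence of any exception in SAP 9.3.

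The number of subjects, and the size and direction of any bias, cannot be derived from the documents. The primary analysis is untouched. This is an inexpensive improvement to exploratory summaries.

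**What to change.** Reword the SAP 9 sentence so that the cut-off reads clearly as 30 days after permanent discontinuation of all study drugs. Then add that it does not apply to the nominal FU-12 visit for SF-36, FACIT-F, CLDQ-HCV and WPAI: all FU-12 forms from subjects who received at least one dose of LDV/SOF are summarised, whatever their study-drug status. The adherence scale and the HIV treatment satisfaction questionnaire concern the HIV regimen itself and can stay under the existing limit.

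The cost is a short SAP edit, with no new data and no protocol change. The downside is that the summaries by HIV treatment group will include a few forms completed off the study HIV regimen; a footnote giving their number per arm deals with that.

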9.1. Analysis of VAS

The VAS (%) absolute value and its change from baseline at Study Baseline, Week 8, Week 20, Week 32 (ie, post HCV treatment Week 4), and End of HIV Treatment (EOT-HIV) will be summarized using descriptive statistics.

Number of days with missed doses in the past 30 days and past 4 days will be summarized categorically (eg, < 2, 2 to < 4, 4 to < 6, ≥ 6 for the past 30 days; 0 and > 0 for the past 4 days) at the same set of visits.

9.2. Analysis of HIV-TSQ

A treatment satisfaction scale total will be calculated as the sum of the responses to the 10 question items on the Status form, ranging from 0 to 60, and on the Change form, ranging from -30 to 30. If the number of missing responses is ≥ 2 then the treatment satisfaction scale total will be set to missing; otherwise, the missing item scores will be imputed by the average of the non-missing item responses from the same subject at the same visit, and treatment satisfaction scale total will be calculated.

Descriptive summary of the number and percent of subjects with responses to each question and the treatment satisfaction scale total at Study Baseline, Weeks 8, 20, and 32, and EOT-HIV will be provided.

